4.10. Primary Analyses

All primary analyses will be performed for the As-Treated population.

4.10.1. Adverse Events

Adverse events will be classified by System Organ Class (SOC) and Preferred Term (PT) using the Medical Dictionary for Regulatory Activities (MedDRA Version 17.0). In order to remain consistent in the adverse event data collected in previous trials, the severity of adverse events will be graded by the investigator according to the CTCAE, Version 3.0 whenever possible. The adverse event CTCAE/severity grades include Grade 1 (Mild), Grade 2 (Moderate), Grade 3 (Severe), Grade 4 (Life-threatening), and Grade 5 (Fatal). The relationship of study drug to adverse event has 4 categories: probable, possible, unlikely and unrelated.

A treatment-emergent adverse event (TEAE) is defined as an adverse event that occurs or worsens in the period extending from the day of a subject's first dose of study drug to 4 weeks after the last dose of study drug in this study. In the following analyses, a subject having the same event more than once will be counted only once. Adverse events will be summarized by worst CTCAE/severity grade.

Total numbers of AEs, TEAEs and serious AEs (SAE) and the number and percentage of subjects experiencing ≥ 1 TEAE, ≥ 1 SAE, discontinuation due to AE, and death will be tabulated. The number and percentage of subjects with TEAEs and SAEs will be by Relationship to study drug and CTCAE/severity, respectively.

The number and percentage of subjects experiencing a specific TEAE will be tabulated

- 1) by SOC, and PT
- 2) by SOC, PT, and CTCAE/severity grade
- 3) by SOC in the descending order of the SOC frequency in ataluren group,
- 4) by PT in the descending order of the PT frequency in ataluren group.

The following TEAEs will be analyzed similarly:

- 1) by SOC, and PT and
- 2) by SOC, PT, and CTCAE/severity grade.
 - Possibly or probably treatment-related TEAEs
 - Serious TEAEs and possibly or probably treatment-related serious TEAEs
 - TEAEs leading to discontinuation from treatment
 - Adrenal, hepatic and renal TEAEs and possibly or probably treatment-related adrenal, hepatic and renal TEAEs leading to special diagnosis evaluation
 - TEAEs with CTCAE/severity grade ≥ 3 and possibly or probably treatment-related TEAEs with CTCAE/severity grade ≥ 3
 - Common TEAEs (subject frequency of $\geq 5\%$)

Listings of death, serious AEs, AEs leading to discontinuation from treatment, and adrenal, hepatic and renal AEs leading to special diagnostic evaluations will be provided. Renal AEs for subjects not using nephrotoxic concomitant medications, subjects using nephrotoxic concomitant medications, and subjects with postbaseline creatinine $> 1.5 \times \text{ULN}$ will also be listed, separately.

The drug exposure adjusted TEAE incidence rate will be summarized by SOC and PT, where the incidence rate of the TEAE per 100 patient-year = (number of events/number of patient-years) $\times 100$. The number of patient-years is defined as the sum of the number of days on study drug of all patients divided by 365.25.

In addition, the number of subjects with clinical laboratory abnormalities, abnormal vital signs, and abnormal electrocardiogram reported as TEAE will be summarized.

Non-serious TEAE will be displayed by SOC and PT. The common non-serious TEAE (subject frequency of $\geq 5\%$) will also be displayed by SOC and PT.

Numbers of occurrence of serious TEAE and the numbers of occurrence of non-serious TEAE will be summarized by SOC and PT, separately.

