## **7. CONCOMITANT AND SUPPORTIVE THERAPY**

### **7.1. Concomitant Medications**

Other than ataluren, any treatments (including prescription and non-prescription drugs, health foods, herbal remedies, self-prescribed drugs, street drug, tobacco products, or alcohol) taken by a subject from the screening period through the 4-Week Post-Treatment Follow-Up Visit are considered concomitant medications. Information regarding all concomitant medications will be collected and documented in the concomitant medication page of the CRF.

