### **7.1.2. Therapy for CF Pulmonary Exacerbations or Other CF Complications**

Subjects should receive appropriate antibiotic or other therapy for CF pulmonary exacerbations or other CF-related complications (eg, DIOS) consistent with local best practices and guidelines. For subjects requiring systemic antibiotic therapy, IV aminoglycosides may be used when medically necessary. However, given ataluren's ribosomal mechanism of action, and the possibility of aminoglycosides exhibiting a confounding effect upon study results, investigators should substitute other antibiotics for systemic aminoglycosides in subjects who require treatment for serious infections whenever possible. For such severe infections, consideration should be given to use of appropriate alternative anti-pseudomonal agents including macrolide and glycopeptide antibiotics. Subjects requiring IV therapy with a glycopeptide antibiotic (eg, vancomycin), should be closely monitored in an appropriate setting, such as a hospital. Based on the increased incidence of creatinine elevation in patients treated with IV aminoglycosides and/or vancomycin, concomitant use of these medications with ataluren is contraindicated. If nephrotoxic antibiotics (eg, tobramycin or vancomycin) are administered, ataluren treatment must be interrupted for the duration of IV antibiotic treatment. In subjects receiving any type of potentially nephrotoxic agents, antibiotic drug levels, and renal function should be closely monitored. Creatinine and BUN should be measured prior to initiating aminoglycosides or other potentially nephrotoxic therapy, and at least twice a week during the course of such antibiotic treatment, where possible. The antibiotic trough level, creatinine and BUN should be measured within 24 to 48 hours of administration of the first antibiotic dose, and further antibiotic dosing should be based on these results. Trough levels should also be measured at intervals during the course of antibiotic treatment, where possible. Additionally, subjects should be adequately hydrated prior to receiving potentially nephrotoxic IV antibiotics, and hydration status should be carefully monitored throughout the administration of these agents. Investigators should be particularly vigilant with subjects experiencing nausea, vomiting, diarrhea, fever, or laboratory evidence of dehydration. Treatment with ataluren may be resumed no earlier than 2 days after administration of nephrotoxic antibiotics has ceased.

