In the Phase 3 clinical trial (Study 009), serious adverse events related to renal dysfunction, which occurred only in the ataluren arm, included 3 patients with acute renal failure, 3 patients with renal failure, and 1 patient with hypercreatininemia. These events were characterized by elevated creatinine (Grade 1 to Grade 4), which resolved over days to weeks. Only 1 patient experienced symptoms of renal dysfunction (transient oliguria). All 7 events were associated with concomitant systemic treatment with potentially nephrotoxic antibiotics (eg, aminoglycosides, vancomycin) that were generally administered as treatment for pulmonary exacerbations. No patient required dialysis. One patient was unblinded and 1 patient chose not to continue study drug treatment; the remaining 5 of 7 patients restarted study medication and continued study participation without recurrent creatinine elevations. This issue was recognized during the conduct of the study and changes were made in the protocol (eg, prohibition of concomitant use of potentially nephrotoxic agents), which successfully addressed the issue. Non-serious creatinine elevations occurred predominantly in the ataluren arm and were transient, generally mild, and resolved with or without interruption of study medication. The incidence of treatment emergent nephrolithiasis was similar in the ataluren and placebo groups.

The renal monitoring program included in this protocol considers nonclinical and clinical findings with ataluren, and past experience with known nephrotoxins. Concomitant use of potentially nephrotoxic antibiotics with ataluren is prohibited. A focus is placed on well-established clinical indicators of renal dysfunction for making diagnostic decisions and prompting treatment interruptions/modifications in individual patients. The rationale for each of the decision-making parameters is discussed below.

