4.8. Prior and Concomitant Medications and Procedures

Prior medications will be defined as those medications that were used prior to the first dose of study treatment. Concomitant medications will be defined as those medications that were used during the study treatment period. If the start date of a medication is missing and the end date is

prior to study start, the medication will be deemed prior. If the end date is after study start or is also missing, the drug will be deemed concomitant. If the end date is missing or the medication is ongoing, the medication will be considered concomitant. If the medication start date is completely missing and end date is missing or ongoing, the medication will be considered both prior and concomitant. Prior and concomitant therapies will be defined similarly.

Prior and concomitant medications will be coded by means of the World Health Organization Drug Dictionary (WHODRUG) into Anatomical-Therapeutic-Chemical classification (ATC) codes. Subject incidence of prior and concomitant medications will be tabulated by ATC level 2 and preferred term for the As-Treated population. Subjects will only count once for each ATC or preferred term in the event that they have multiple records of the same ATC or preferred term in the database.

Prior and concomitant non-drug therapies will be coded and analyzed similarly.

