4.9. Study Treatment Administration and Compliance

The study treatment duration in weeks is defined as $(\text{last dose date} - \text{first dose date} + 1)/7$ and will be summarized overall. This duration is irrespective of the dose interruptions.

The drug compliance of a specific time period is defined as $100 * (\text{number of sachets taken during the period} / \text{number of planned sachets during the period})$. It will be summarized for overall treatment duration. The percentages will take into account physician-prescribed reductions and interruptions.

The number and percentage of subjects having dose interruptions and dose changes will be summarized using descriptive statistics for overall treatment duration.

The above analyses will be performed for the As-Treated population.

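### SAP 4.10.1 sorts renal adverse events by whether the subject used a nephrotoxic drug, not by whether one was being taken near the event

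*SAP*

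**What the plan says.** SAP 4.10.1 asks for three separate listings of renal adverse events. Two are defined by co-medication: "Renal AEs for subjects not using nephrotoxic concomitant medications, subjects using nephrotoxic concomitant medications". The third covers subjects whose post-baseline creatinine exceeded 1.5 x ULN. In all three the unit is the subject, and the section does not relate drug dates to event onset.

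What counts as concomitant comes from SAP 4.8: "Concomitant medications will be defined as those medications that were used during the study treatment period". The same section adds: "If the end date is missing or the medication is ongoing, the medication will be considered concomitant". SAP 4.9 measures treatment from first to last dose and says: "This duration is irrespective of the dose interruptions". The treatment-emergent window in SAP 4.10.1 is longer, running "to 4 weeks after the last dose of study drug in this study".

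Protocol 7.1 uses a wider definition, under which treatments "taken by a subject from the screening period through the 4-Week Post-Treatment Follow-Up Visit are considered concomitant medications". SAP 1 says that the SAP prevails where the two conflict. SAP 6, which lists the changes from the protocol, does not mention this narrowing.

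Protocol 7.1.2 provides that when nephrotoxic IV antibiotics are given, "ataluren treatment must be interrupted for the duration of IV antibiotic treatment".

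**The concern.** The kidney is the organ of main concern for this drug. Protocol 14.2.3.1.1 reports that the serious renal-dysfunction events in Study 009 occurred only on ataluren, and that all 7 were associated with potentially nephrotoxic systemic antibiotics. A reader of the Study 023 report will therefore ask whether renal events also occur when no such antibiotic is on board. These two listings are the only SAP output that separates renal adverse events by nephrotoxic co-medication.

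That question concerns each event and its timing, but the listings answer a question about each subject. An event with no nephrotoxic drug near its onset can appear under *using*, and in narrower circumstances an event that followed such a drug can appear under *not using*.

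**Working it through.** The plan states no figure on this point, so there is none to reproduce. The check sets the definitions side by side and then adds an illustration.

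**Definitions.**
- SAP 4.8, concomitant: used during the study treatment period. Under SAP 4.9 treatment runs from first to last dose, and SAP Table 1 shows the 4-week follow-up as a separate period.
- SAP 4.10.1, treatment-emergent: first dose to last dose plus 28 days.
- Protocol 7.1, concomitant: screening through the 4-week follow-up visit.

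**Case A: a nephrotoxic course during treatment, ataluren restarted.** The course lies between first and last dose, because SAP 4.9 ignores interruptions. The drug is concomitant and the subject is a user. A renal event near the course is correctly listed. A renal event a year away from it goes into the same listing.

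**Case B: a nephrotoxic course only after the last ataluren dose.** This arises if ataluren is interrupted and never restarted, or if the course begins after ataluren has been stopped for good. With complete start and stop dates the drug is neither prior nor concomitant under SAP 4.8. A renal event within 28 days of the last dose is still treatment-emergent, but it is listed under *not using*. All of the following must hold:
1. The drug starts after the final ataluren dose.
2. Its dates are complete. A missing start or end date, or an ongoing drug, makes it concomitant.
3. The subject had no other nephrotoxic drug during treatment.

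**Illustration for Case A.** Inputs: treatment of 64 weeks (the threshold for the second interim review) or 192 weeks (as planned), and 28 days of follow-up, all from the documents. Assumptions: K non-overlapping antibiotic windows of w days each, and an unrelated renal event equally likely on any day of the treatment-emergent window.

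Treatment-emergent window W = 7 x weeks + 28:
- 64 weeks: 448 + 28 = 476 days
- 192 weeks: 1344 + 28 = 1372 days

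Share of W outside the antibiotic windows = 1 - K x w / W:

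| Treatment | K | w = 14 days | w = 42 days |
|---|---|---|---|
| 64 weeks | 1 | 1 - 14/476 = 97% | 1 - 42/476 = 91% |
| 64 weeks | 4 | 1 - 56/476 = 88% | 1 - 168/476 = 65% |
| 192 weeks | 1 | 1 - 14/1372 = 99% | 1 - 42/1372 = 97% |
| 192 weeks | 4 | 1 - 56/1372 = 96% | 1 - 168/1372 = 88% |

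These shares apply only to unrelated events in subjects who are already users. They are not shares of all renal events.

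**Extent of Case B.** The 28 days after the last dose are 28/476 = 5.9% of the window at 64 weeks and 28/1372 = 2.0% at 192 weeks. That bounds the time in which Case B can arise, not the number of events, since events may cluster after an antibiotic.

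**The case against.** The strongest reply is that these are supplementary listings in a single-arm descriptive study of about 70 subjects. No count, rate or test rests on the split. SAP 4.1 lists every CRF module by subject, and onset dates and medication dates are collected, so a reader can rebuild the timing case by case. Investigators already grade each event's relationship to ataluren and weigh concomitant drugs in doing so (Protocol Table 4). The creatinine listing applies regardless of co-medication. All of this stands, and it limits the consequence. It does not make the two listing headings say what was happening at onset.

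A second reply is that the SAP never says *ever used*. It gives no time window, so a programmer might apply one. That is fair, but grouping by subject is the plain reading of the text, and no other rule is offered.

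A third is that the SAP leaves the study treatment period undefined in section 4.8, so the protocol's wider definition might be read into it. This is arguable, but SAP Table 1 separates treatment from follow-up, and SAP 1 gives the SAP precedence where the two conflict.

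A reader might also infer a size for Case B from Study 009, where "the remaining 5 of 7 patients restarted study medication", leaving 2 of 7, or 29%. The documents do not support that transfer. Protocol 14.2.3.1.1 describes the antibiotics in all 7 events as concomitant treatment, so those subjects would be listed under *using*. Not restarting after an event does not show that the antibiotic began after the last dose. With 7 patients the exact 95% interval would in any case be 4% to 71%.

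**Conclusion.** The point holds as a weakness in how the listing is specified. The main effect is that unrelated renal events in subjects with any nephrotoxic course during treatment are listed under *using*. The reverse error is real but needs several conditions at once.

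The size is unknown. Neither document gives a rate of nephrotoxic courses, and the protocol restricts such drugs with ataluren. A reader might assume a rate and derive the share of all renal events that would be misfiled, but nothing in the documents fixes that rate. The 91% to 97% for one window at 64 weeks illustrates how little of a user's follow-up a single course covers. It rests on the assumed window length and evenly timed events.

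A reader might also conclude that the listings could create or hide a renal signal. That goes too far, since the outputs are descriptive and the timing can be recovered from other listings. I would class this as a cheap improvement.

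**What to change.** Amend SAP 4.10.1 before database lock, as SAP 1 allows:
- Classify each renal event, not each subject, by whether a nephrotoxic agent was taken on the onset date or within a prespecified look-back window before it.
- Fix the list of agents that count. The protocol gives only examples, and the SAP names none for this listing.
- Count agents through the 4-week follow-up visit, by aligning SAP 4.8 with Protocol 7.1 and the treatment-emergent window.
- Print the agent, its start and stop dates, and whether ataluren was being taken, interrupted or stopped at onset beside each event.

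The cost is SAP wording and one reprogrammed listing. No new data are needed, and nothing changes for subjects or sites. The look-back length is somewhat arbitrary, but with the dates printed a reader can apply another.

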#### **8.2.2.2. Post-Treatment Visits**

All subjects, including those who discontinue study drug prematurely, will return to the investigational site 4 weeks ( $\pm 7$  days) after the last dose of ataluren for a 4-Week Post-Treatment Follow-up Visit. Please refer to [Section 10](#) for further details regarding subject withdrawal procedures. The end of trial will be defined as the date the last subject completes the last study visit, which is expected to be the 4-Week Post-Treatment Follow-up Visit.

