#### **8.2.12. Adverse Events**

Adverse events must be assessed and documented at each clinic visit. This information will be collected at Week 1 (Visit 2) through Week 196 (Visit 15 - Post-Treatment Visit; 4 weeks post discontinuation of study drug). In addition, subjects/caregivers will be encouraged to report adverse events of concern at any time in the intervals between visits. Refer to [Section 9](#) for additional information regarding adverse event collection and reporting.

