## 9.8. Adverse Event Reporting Period

The first day of adverse event reporting will coincide with the day the first dose of ataluren is administered. The adverse event reporting period for this study ends with the 4-Week ( $\pm$  7 days) Post-Treatment Follow-up visit, except as described in [Section 9.7](#). In addition, SAEs occurring in a subject after the study period should be reported to the sponsor if the investigator becomes aware of them.

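### The exposure-adjusted TEAE rate in SAP 4.10.1 counts events to 4 weeks after the last dose but divides by on-drug time only

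*SAP*

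**What the plan says.** SAP 4.10.1 defines a treatment-emergent adverse event (TEAE) as one that occurs or worsens from the day of the "first dose of study drug to 4 weeks after the last dose of study drug in this study". Protocol 11.4.5.1 uses the same window. The SAP then adds a drug-exposure-adjusted rate by SOC and PT: "the incidence rate of the TEAE per 100 patient-year = (number of events/number of patient-years"), multiplied by 100. On the denominator it says: "The number of patient-years is defined as the sum of the number of days on study drug of all patients divided by 365.25".

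The protocol collects events throughout the post-treatment part of that window:

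- Section 8.2.2.2: "All subjects, including those who discontinue study drug prematurely, will return to the investigational site 4 weeks" (±7 days) after the last dose.
- Section 8.2.12: "This information will be collected at Week 1 (Visit 2) through Week 196", which is the post-treatment visit.
- Section 9.8: "The adverse event reporting period for this study ends with the 4-Week" follow-up visit.

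Two neighbouring rules bear on how the rate would be programmed. SAP 4.9 defines treatment duration from first to last dose and adds: "This duration is irrespective of the dose interruptions". SAP 4.10.1 also says: "In the following analyses, a subject having the same event more than once will be counted only once". SAP 6 lists the exposure-adjusted rate as an addition to the protocol analyses.

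**The concern.** An incidence rate needs the same time window above and below the line. Here the events come from treatment plus 28 days and the person-time from treatment only. The result is neither a rate on drug nor a rate over the TEAE window.

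Exposure adjustment is meant to make rates comparable across different lengths of treatment. This formula makes the stated rate depend on treatment length: for the same underlying rate, shorter exposure gives a higher figure. SAP 2.1 says that all ongoing subjects are discontinued when the study is terminated early, so exposure will fall short of plan and the distortion will grow. Event frequency is part of the primary endpoint, and Protocol 14.1.3.1 keeps the same CTCAE version to allow comparison with earlier ataluren trials, so readers are likely to set this rate beside others.

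There is also a wording point. The counted-once sentence is said to apply to the analyses that follow, and this rate is one of them, yet the formula uses the number of events. Protocol 11.4.5.1 confines counting once to the by-subject analysis; the SAP dropped that limit. Counting every event is the natural reading, but the text should say so.

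**Working it through.** The plan states no rate and no patient-year total, so there is no figure to reproduce. The check is direct arithmetic.

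**Inputs**

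- Time after the last dose in the numerator: 28 days (SAP 4.10.1).
- Follow-up visit window: ±7 days (Protocol 8.2.2.2), so follow-up could end at day 21.
- Subjects: about 70 (SAP 2.4).
- Planned treatment: about 192 weeks, or 1,344 days (SAP 2.1).
- Mean exposure after early termination: not given. I assume 48, 96, 144 and 192 weeks to show the range.
- Days on study drug are read as last dose − first dose + 1, as in SAP 4.9.

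**Formula**

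Let E be the number of TEAEs and D a subject's days on drug.

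- Rate as written: 100 × E / (ΣD / 365.25)
- Rate matched to the window, full follow-up: 100 × E / (Σ(D + 28) / 365.25)
- Ratio: Σ(D + 28) / ΣD = 1 + 28 / mean D

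E cancels, so against the window-matched rate the ratio holds whatever the event rate after the last dose.

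**Results**

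| Mean exposure | 28 days of follow-up | 21 days of follow-up |
|---|---|---|
| 48 weeks (336 days) | 28/336 = 8.3% | 21/336 = 6.3% |
| 96 weeks (672 days) | 28/672 = 4.2% | 21/672 = 3.1% |
| 144 weeks (1,008 days) | 28/1,008 = 2.8% | 21/1,008 = 2.1% |
| 192 weeks (1,344 days) | 28/1,344 = 2.1% | 21/1,344 = 1.6% |

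Person-time left out with 70 subjects: 70 × 28 / 365.25 = 5.4 patient-years. On-drug time is 70 × 336 / 365.25 = 64.4 patient-years at 48 weeks and 70 × 1,344 / 365.25 = 257.6 at 192 weeks.

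As an illustration, a window-matched rate of 50 per 100 patient-years (an assumed value) would be stated as 50 × 1.0833 = 54.2 at 48 weeks, 50 × 1.0417 = 52.1 at 96 and 50 × 1.0208 = 51.0 at 192.

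**Against a different target, the pure on-drug rate**

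If the event rate after the last dose is k times the on-drug rate, the excess is k × 28 / mean D. At 96 weeks this is 0% for k = 0, 2.1% for k = 0.5, 4.2% for k = 1 and 8.3% for k = 2.

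**Interruptions**

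SAP 4.10.1 does not tie its denominator to the duration in SAP 4.9. If a programmer subtracted interrupted days, the gap would widen. Assuming 16 such days per 48 weeks, the overstatement would be (336 + 28) / (336 − 16) − 1 = 13.7% at 48 weeks and (1,344 + 28) / (1,344 − 64) − 1 = 7.2% at 192 weeks.

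**The case against.** The best defence is that the statistic is labelled as adjusted for drug exposure, and on-drug days are drug exposure. Both components are openly defined, and the SAP never claims to estimate a rate over treatment plus 28 days. Either repair changes the statistic: extending person-time turns drug exposure into observation time, and restricting onset drops events that the SAP itself calls treatment-emergent. The excess over the on-drug rate depends on what happens after the last dose and is nil if nothing does. There is one treatment group, SAP 4.2 calls all analyses descriptive, and the error runs in the cautious direction for a safety study.

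Much of this stands as a limit on the weight of the point. The size against the on-drug rate is conditional, the actual exposure is unknown, and the choice between the two repairs is partly preference. The counted-once sentence is not a firm contradiction either, since it can be read as a rule about counting subjects and the SAP tabulates occurrences separately.

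The core of the defence fails. The label explains the denominator, but it does not make a numerator that includes off-drug events match it. Against the rate for the window in which the events are counted, the overstatement does not depend on the event rate after the last dose.

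**Conclusion.** The rate is wrong as written: its numerator and denominator cover different periods, and nothing in either document reconciles them. The overstatement relative to the window-matched rate ranges from 2.1% at the planned 192 weeks to 8.3% at a mean of 48 weeks. This assumes complete 28-day follow-up and person-time that includes interruptions; shorter follow-up lowers it and shorter exposure raises it. The point is minor. It affects one descriptive summary and leaves the subject-incidence and occurrence tables, and any decision about the study, unchanged. Confidence that the mismatch exists is high; its realised size cannot be fixed from the documents.

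**What to change.** Amend SAP 4.10.1 in one of two ways:

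1. Define patient-years as the sum over subjects of [min(last dose + 28 days, last contact, death) − first dose + 1] / 365.25, without subtracting interruptions, in line with SAP 4.9. The table should then be labelled as a rate over the TEAE window.
2. Keep last dose − first dose + 1 as person-time and count only events with onset from first to last dose. Events after the last dose then leave this table but remain in the other TEAE tables.

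In the same edit, state that this table counts every TEAE occurrence and that the counted-once rule applies to by-subject tables only, as in Protocol 11.4.5.1.

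The cost is two sentences and a small change to the denominator or numerator program, with slightly lower stated rates. No new data are needed, and SAP 1 allows such refinements by amendment before database lock.
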